8.2.2 Immunological evaluation

(f) Change from baseline in CD4, CD8, and CD4/CD8 ratio over 96 weeks with evaluation at week 24, 48, and 96.

The evolution of the CD4, CD8 and CD4/CD8 ratio over 96 weeks according to the treatment group will be described by boxplots for each treatment group at each visit. The changes will also be compared between the two treatment group using mixed models for repeated measures with random intercept and unstructured covariance matrix, adjusted for baseline value. The models will include treatment group, time, interaction between treatment group and time, and baseline value. Time will be considered as categorical variable (0, 12, 24, 48, 72 and 96 weeks) according the planned study visits. Visits window are shown in Table A (section 6.2). Data will be also summarised in tables by mean and standard error.

If the residual of the mixed model is not normally distributed and therefore does not allow the use of parametric test, the changes from baseline to week 24, 48 and 96 of CD4 T cell count, CD8 T cell count and CD4/CD8 ratio will be compared between the 2 groups using Mann-Whitney-Wilcoxon test.

9. Safety analyses:

(g) Number and percentage of participants with adverse events (AEs), severity of AEs, and treatment discontinuations due to AEs.

Adverse events (AE), especially grade 3 and 4 AE, serious adverse events (SAE), drug-related AE (all grades), treatment interruption due to AE (all grades), pregnancies and death will be summarized with descriptive statistics. The incidence rates of the events defined above will be compared between the treatment groups using a Poisson regression analysis which accounted for all adverse events and follow-up duration for each participant. The Poisson regression models will include the number of events, the treatment group and the duration of exposure in year in log. The number and percentage of death as well as the causes of death will be given. The number and percentage of pregnant women will also be given. A table will summarize the frequency of adverse events and pregnancies. This table will include the name of event, number and percentage of patients with events, number of events, and incidence rate (IR) per 100 person-years in the DTG/RPV group and the control group respectively, and incidence rate ratio (IRR) and 95%CI for IRR. All grades 3 or 4 AE related to the study drugs and treatment interruption due to AE will be put in the table.

(h) Changes from baseline in laboratory parameters at week 24, 48 and 96.

The evolution of haematology parameters (including haemoglobin, white cell count and differential, platelets) and biochemistry parameters (including sodium, glucose, ALT, AST, and total bilirubin) according to the treatment group will be described by boxplots for each treatment group at baseline, week 24, 48 and 96. The changes from baseline will be compared between the two treatment groups

using mixed models for repeated measures with random intercept and unstructured covariance matrix adjusted for baseline value. The model will include treatment group, time and interaction between treatment group and time, and baseline value. Time will be considered as categorical variables. Data will be also summarised in tables by mean and standard error.

If the residual of the mixed model is not normally distributed and therefore does not allow the use of parametric test, the non-parametric Mann-Whitney-Wilcoxon test will be used to compare the changes from baseline to week 24, 48 and 96 between the two treatment groups.

(i) Changes from baseline in renal markers, bone markers, and fasting lipids at week 24, 48 and 96.

The evolution of renal markers (including blood creatinine, blood creatinine clearance (eGFR), urine creatinine, urine protein, urine protein/creatinine ratio, blood albumin, urine albumin, urine albumin/creatinine ratio, urine beta 2 microglobulin, urine creatinine clearance (eGFR), potassium, blood phosphate, urine phosphate), bone markers (including ALP) and lipids fasting parameters (including total cholesterol, HDL, LDL, triglycerides) according to the treatment group will be described by boxplots for each treatment group at baseline, week 24, 48 and 96.

The changes from baseline will be compared between the two treatment groups using mixed models for repeated measures with random intercept and unstructured covariance matrix adjusted for baseline value. The model will include treatment group, time and interaction between treatment group and time, and baseline value. Time will be considered as categorical variables. Data will be also summarised in tables by mean and standard error.

If the residual of the mixed model is not normally distributed and therefore does not allow the use of parametric test, the non-parametric Mann-Whitney-Wilcoxon test will be used to compare the changes from baseline to week 24, 48 and 96 between the two treatment groups.

10. Pharmacokinetics

[figure not shown]
(j) Pharmacokinetic assessment

Pre-dose plasma concentrations of DTG and RPV at week 4 (experimental arm only), 48 (experimental arm only) and 96. Plus pre/post-dose (as appropriate) at early termination visit and /or in the event of virological failure a post dose sample will be taken within 20-28 hours.

At each time point, the AUC of DTG and RPV post administration will be summarized by the median, Q1, Q3, min, max and number of non-missing values. For each drug, we will compare the evolution of AUC over time using Wilcoxon paired test.

We will use the trapezoidal approach to calculate the area under the curve (AUC). For example, given data t_0, t_1, \dots, t_N and y_0, y_1, \dots, y_N , the area under the curve can be approximated as follows:

$$\int_a^b f(x) dx \approx \frac{1}{2} \sum_{i=1}^N (t_i - t_{i-1})(y_i + y_{i-1})$$
 where t_i is the time value and y_i is the concentration of the antiretroviral drug.

(k) Number of potential DDIs avoided assessment

The number of potential DDIs avoided will be calculated by the difference between the number of interaction drugs graded “amber or red” before and after switching to dolutegravir and rilpivirine. More details are shown in section 3.2.2. The number of DDI avoided will be compared between the two-treatment groups using Mann-Whitney Wilcoxon test. Data will be summarized by the median, Q1, Q3, min, max and number of non-missing values.

11. Other analyses

(l) Changes in quality of life from baseline to week 24, 48 and 96.

The EQ-5D-3L quality of life questionnaires will be analysed using multiple imputation approach to replace missing values (assumption: Missing At Random). Multiple imputation using Chained Equations approach (MICE) will be used to fill in missing data. Therefore, we will create 10 datasets, in which missing data will be imputed from each patient’s other covariables, including all items in the questionnaires, to obtain valid inference and reduce sampling variability resulting from the imputation process. The analysis will include all participants from the mITT population that will complete at least one of the 4 questionnaires (baseline, weeks, 24, 48, and 96). Participants with more than 20% missing data in a specific questionnaire will be excluded from the analysis of the questionnaire.

The changes from baseline will be compared between the two treatment groups using mixed models for repeated measures with random intercept and unstructured covariance matrix adjusted for baseline value. The model will include treatment group, time and interaction between treatment group and time, and baseline value. Time will be considered as categorical variables. Analyses will be run on each of the 10 datasets, including the imputed values, and the results will be combined with Rubin’s rules. The p-values will be two-tailed, with a significant level of 0.05. Data will be summarised in tables by the mean and standard error.

To assess the impact of study treatment in the evolution of each of the 5 dimensions (mobility, self-care, usual activities, pain/discomfort and anxiety/depression), a generalized estimating equation (GEE) model with a multinomial distribution (if 3 levels) or binomial distribution (if 2 levels) will be used. Each dimension: mobility, self-care, usual activities, pain/discomfort and anxiety/depression will be used as qualitative variables. If the numbers of reported level 3 problems are very low, we will group together level 2 and 3. Analyses will be run on each of the 10 datasets, including the imputed values, and the results will be combined with Rubin’s rules. The model will include treatment group, time and interaction between time and treatment group, and baseline score as covariate. Time will be considered as categorical variable. The p-values will be two-tailed, with a significant level of 0.05.

(m) Changes in patient satisfaction from baseline.

The patients' satisfaction will be evaluated by self-reported questionnaires at baseline (HIVTSQs (status)) and post-baseline (HIVTSQc (change)) at weeks 24, 48 and 96. Each questionnaire include 12 items scored from 0 (dissatisfied) to 6 (satisfied) for HIVTSQs and scored from -3 (much less satisfied now) to 3 (much more satisfied now) for HIVTSQc. A global satisfaction score will be calculated at each time point by summing the result of the 12 items, leading to a global HIVTSQs score at baseline ranging from 0 to 72 (72 being higher satisfaction) and global HIVTSQc (change) post-baseline score ranging from -36 to 36 (36 being much more satisfaction). The analysis will include all participants from the mITT population that will complete at least one of the 4 questionnaires (baseline, weeks, 24, 48, and 96). We will compare the patients' satisfaction score post-baseline between the two treatment groups using mixed models for repeated measures with random intercepts and unstructured covariance matrix, adjusted for patients' baseline satisfaction score (HIVTSQs). The models will include treatment group, time and interaction between treatment group and time, and patients' baseline satisfaction score as covariate. Time will be considered as categorical variables. Data will be also summarised in tables by mean and standard error.

(n) Pittsburgh Sleep Quality Questionnaire

The Pittsburgh Sleep Quality Index (PSQI) contains 19 questions on the participant and 5 questions on the bed partner or roommate (if one is available). Only questions on the participant are included in the scoring. The 19-participant items are combined to form seven "component" scores, each of which has a range of 0-3 points. In all cases, a score of "0" indicates no difficulty, while a score of "3" indicates severe difficulty. The seven component scores are then added to yield one "global" score, with a range of 0-21 points, "0" indicating no difficulty and "21" indicating severe difficulties in all areas. The seven components are: component 1 (Subjective sleep quality); component 2 (Sleep latency); component 3 (Sleep duration); component 4 (Habitual sleep efficiency); component 5 (Step disturbances); component 6 (Use of sleeping medication); component 7 (Daytime dysfunction). Appendix shows how to calculate each component score.

As some data will be missing and because it is better to input than to ignore them, a multiple imputation using Chained Equations approach (MICE) will be used to fill in missing data. Ten imputations (M=10) will be chosen to obtain valid inference and reduce sampling variability resulting from the imputation process.

This analysis will include all participants from the mITT population that will complete at least one of the 4 questionnaires (baseline, weeks, 24, 48, 72, and 96). In each questionnaire, participants with more than 20% of missing data will be excluded from the analysis of the questionnaire.

The changes from baseline to week 24, 48, 72 and 96 will be compared between the 2 groups using mixed models for repeated measures with random intercept and unstructured covariance matrix, adjusted for patients' baseline score. The models will include treatment group, time and interaction between treatment group and time, and patients' baseline score as covariate. Time will be considered

as categorical variables. Analyses will be run on each of the 10 datasets, including the imputed values, and the results will be combined with Rubin's rules. The p-values will be two-tailed, with a significant level of 0.05. Data will be also summarised in tables by mean and standard error.

(o) Changes from baseline in hsCRP over 96 weeks with evaluation at week 24, 48 and 96

The evolution of hsCRP over 96 weeks according to the treatment group will be described by boxplots for each treatment group at baseline, weeks 24, 48 and 96.

The changes from baseline will be compared between the two treatment groups using mixed models for repeated measures with random intercept and unstructured covariance matrix adjusted for baseline value. The model will include treatment group, time and interaction between treatment group and time, and baseline value as covariate. Time will be considered as categorical variables. Data will be also summarised in tables by mean and standard error.

If the residual of the mixed model is not normally distributed and therefore does not allow the use of parametric test, the non-parametric Mann-Whitney-Wilcoxon test will be used to compare the changes from baseline to week 24, 48 and 96 between the two treatment groups.

12. Reporting Conventions

P-values ≥ 0.001 will be reported to 3 decimal places; p-values less than 0.001 will be reported as " <0.001 ". The mean, standard deviation, and any other statistics other than quantiles, will be reported to one decimal place greater than the original data. Quantiles, such as median, or minimum and maximum will use the same number of decimal places as the original data. Estimated parameters, not on the same scale as raw observations (e.g. regression coefficients) will be reported to 3 significant figures.

13. Technical Details

Data will be summarised using the IBM SPSS® statistics software version 24. The non-parametric analyses will be performed also with IBM SPSS statistics software version 24. The Poisson regression analysis, PK analysis and Figures will be done using Stata® SE software version 13. Generalised estimating equation and mixed models will be performed using SAS® software version 9.4.

14. References

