8.2.3 Collection and follow up of Adverse Events

All adverse events, however minor, will be documented in the CRF whether or not the Investigator considers the event to be treatment related.

The adverse event reporting period will be from consent until the subject's final study visit (i.e. follow-up visit or end of trial visit). In addition, any untoward event that may occur subsequent to the reporting period that the Investigator assesses as possibly, probably or definitely related to the study drug medication should also be reported as an Adverse Event.

CONFIDENTIAL

Adverse events may be directly observed, reported spontaneously by the subject or by questioning the subject at each study visit.

All adverse events should be followed up until they are resolved or the subject's participation in the study ends (i.e. until the final CRF is completed for that subject). In addition, all serious and non-serious adverse events assessed by the Investigator as possibly related to the investigational medication should continue to be followed until resolution, or until no further change can reasonably be expected.

Rash and any associated symptoms should be reported as adverse events (see section 6.12)

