4.1 General Study Design and Plan

This trial is an open-label, randomised, 2 arms, parallel-group, multicentre trial, comparing an immediate versus a deferred switch from a boosted PI containing regimen to a dual therapy with DTG and RPV in HIV infected patients with a history of virological failure with NNRTIs or baseline transmitted drug resistance and having developed a K103N mutation. The trial will be conducted within the NEAT ID network and include sites in 7 countries that have an excellent track record in clinical research. After screening, participants will be randomised 2:1 to switch to DTG/RPV at baseline or at 48 weeks.

The intervention will consist of immediate switch to DTG 50 mg OD + RPV 25 mg OD regimen at baseline or maintaining the current antiretroviral therapy for 48 weeks. At week 48, all participants in the deferred switch group with virological success will be switched to DTG 50 mg OD + RPV 25 mg OD therapy, and all participants will be followed for additional 48-weeks until week 96 (see figure).

After the screening visit, participants will be seen at baseline, weeks 4, 12, 24, 48, 52, 60, 72, 96, and either a follow-up visit (30 days (+/- 7 days) after week 96 visit) or an early termination visit. A week 60 visit may be an optional visit and performed for subjects on the control arm (3 months after therapeutic modification) as required per national guidelines. At each visit, participants will have routine investigations and will include viral load, CD4 & CD8, haematology (including haemoglobin, white cell count and differential, platelets), biochemistry (including sodium, potassium, creatinine, albumin, glucose, ALT, AST, ALP, total bilirubin, total cholesterol, HDL, LDL, triglycerides), PK, PBMC, quality of life questionnaires, patient satisfaction questionnaire, Pittsburgh sleep questionnaire, DDI assessment & urine sample (for haematuria, proteinuria, glycosuria, leukocytes) for full list of investigations please see section 4.4.

Statistical Analysis Plan

WISARD Study Protocol

Haematology Including:
 
 • Platelet count • RBC Count (indices MCV & MCH) • WBC count (absolute) • Haemoglobin • Hamatocrit RBC 
Count indices:
 
 • MCV • MCH 
Automated WBC differentials:
 
 • Neutrophils • Lymphocytes • Monocytes • Eosinophils • Basophils 	x	x	x	x	x	x	x	x	x	

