
Clinical chemistry (Fasted for at least 10 hours except for screening) Including:
 
 • Urea • Chloride • Alkaline phosphatase • Creatine phosphokinase • Creatinine • Calcium • Phosphate • Glucose (optional in 	x*	x*	x	x	x*	x*	x	x	x	x

urine if agreed with sponsor in writing)
 
 • Total bilirubin • Potassium • HsCRP (optional if agreed with sponsor in writing) • Total protein • Sodium • ALT • Albumin • Creatinine clearance (Calculations: Cockcroft-Gault (requires weight), MDRD, CKD-Epi) 
(* including urinary chemistry)
										

Statistical Analysis Plan

WISARD Study Protocol

Fasting Lipids (Fasted for at least 10 hours except at screening) Including: • Total cholesterol • HDL cholesterol • LDL cholesterol • Triglycerides	x	x	x	x	x	x	x	x	x	x	x	x	
HIV RNA viral load		x	x	x	x	x	x	x	x	x		x	
Predose Pharmacokinetic assessment (A post-dose sample will be taken at early termination visit and/or in the event of virological failure within 20-28 hours of last dose)			x (Experimental arm only)				x (Experimental arm only)				x		x
Blood sampling for PBMC isolation (Required unless exemption documented in site contract i.e. if site does not have capacity to process PBMC samples)		x					x				x		x
Quality of Life Questionnaire		x			x	x					x		x
Patient Treatment Satisfaction Questionnaire		x			x	x					x		x
Pittsburgh Sleep Questionnaire		x			x	x					x		x
DDI Assessment		x			x	x					x		x
Adherence Assessment (Self report at visit) (including date and time of last dose on PK days, including ETV visit and/or in the event of virological failure)		x	x	x	x	x	x	x	x	x			x
AE Assessment		x	x	x	x	x	x	x	x	x	x		x
Con Med Check	x	x	x	x	x	x	x	x	x	x			x

5. Sample Size calculation

This is a pilot proof of concept study to investigate whether complex regimens taken by patients with resistance mutations can be replaced by a simple two class single pill regimen safely in terms of viral load and adverse events.

No formal sample size calculation is performed. It is anticipated that data from 150 participants is adequate to meet the trial objectives (100 in the DTG/RPV arm and 50 in the control arm). The expected success rate is 95% based on the data reported by the SWORD 1 & 2 studies (1). If the observed success rate is 95% in the DTG/RPV arm at week 48 and varies from 95% to 100% in the

Statistical Analysis Plan

WISARD Study Protocol

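### SAP 9(g) compares adverse-event rates by Poisson regression on all events with no allowance for repeat events in the same person, so rate-ratio intervals for frequent events will be too narrow

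*SAP*

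**What the plan says.** SAP section 9(g) covers adverse events (with emphasis on grades 3 and 4), serious events, drug-related events of all grades, interruptions due to adverse events, pregnancies and deaths. Incidence rates are to be compared between arms "using a Poisson regression analysis which accounted for all adverse events and follow-up duration for each participant". The terms are then listed: "The Poisson regression models will include the number of events, the treatment group and the duration of exposure in year in log".

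The summary table is to show the number and percentage of patients with an event and, separately, the "number of events, and incidence rate (IR) per 100 person-years" in each group, followed by the "incidence rate ratio (IRR) and 95%CI for IRR". Repeat events in one person therefore enter the rate.

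SAP section 13 covers software: "The Poisson regression analysis, PK analysis and Figures will be done using" Stata SE 13. It names no variance option. Protocol section 8.2.3 sets the breadth of capture: "All adverse events, however minor, will be documented in the CRF".

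**The concern.** A Poisson model sets the variance of each participant's count equal to its mean. That holds only if everyone in an arm, given exposure, has the same underlying event rate. It is unlikely here. All events are recorded regardless of severity, participants are questioned at each visit, and they enter on different regimens with different co-medication. The model has no covariate other than arm. Some people will report many events and most will report few. The variance then exceeds the mean, and the model-based standard error of the log rate ratio is too small.

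The rate ratio is the only between-arm inference the SAP plans for adverse events, and protocol section 9.1 makes safety with respect to adverse events part of the trial's purpose. An interval that is too short can present chance as harm from the switch, or as benefit.

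The SAP allows for within-person correlation elsewhere: GEE for compliance (7.6) and mixed models for HIV DNA, CD4 and laboratory data (8.2 and 9). It also gives a fallback when mixed-model residuals are not normal. The Poisson model has neither.

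**Working it through.** Neither document states an adverse-event rate, dispersion, rate ratio or power for this comparison, so there is no planned figure to reproduce. The check shows what the specified model does over a range of assumptions.

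**Inputs from the documents.** Arm sizes are "100 in the DTG/RPV arm and 50 in the control arm" (SAP section 5). The randomised comparison lasts 48 weeks, or 48/52.18 = 0.92 year (SAP 4.1). Expected loss to follow-up is 15% (protocol 6.12).

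**Assumptions.** These are the mean number of events per participant, μ, and the between-participant variance of the underlying rate relative to its mean squared, φ (gamma heterogeneity).

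**Formulas.**
- Model-based: Var(log IRR) = 1/(100μ) + 1/(50μ).
- With heterogeneity: Var(Y) = μ + φμ², so the true variance is larger by the variance-to-mean ratio, VMR = 1 + φμ.
- Correct width relative to Poisson width, on the log scale: √VMR.
- True type I error of a nominal 5% test: 2 × [1 − Φ(1.96/√VMR)].

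**Type I error, 100 versus 50, no true difference** (simulation with 8,000 runs per cell):

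| μ | φ | VMR | √VMR | Formula | Simulated |
|---|---|---|---|---|---|
| 1 | 0.25 | 1.25 | 1.12 | 8.0% | 8.1% |
| 1 | 1 | 2 | 1.41 | 16.6% | 16.4% |
| 2 | 0.5 | 2 | 1.41 | 16.6% | 16.4% |
| 4 | 0.5 | 3 | 1.73 | 25.8% | 25.5% |
| 4 | 1 | 5 | 2.24 | 38% | 38.5% |

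With robust standard errors, the simulated type I error was 5.4% to 6.3%. A smaller run of negative binomial regression (500 per cell) gave about 4% to 5%.

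**Coverage of the nominal 95% interval.** This was a separate simulation with 48 weeks of exposure, 15% early loss, a true ratio of 1 and 3,000 runs per cell. The formula value, which assumes full exposure, comes first and the simulated value is in brackets.

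| Events per person-year | φ = 0 | φ = 0.5 | φ = 1 | φ = 2 |
|---|---|---|---|---|
| 0.2 | 95% (96%) | 94% (95%) | 93% (95%) | 91% (92%) |
| 1 | 95% (95%) | 90% (89%) | 84% (85%) | 76% (76%) |
| 2 | 95% (95%) | 84% (84%) | 76% (75%) | 64% (64%) |
| 4 | 95% (95%) | 76% (76%) | 64% (66%) | 50% (50%) |

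Robust variance gave 93% to 96% in every cell of this table.

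**One case in full.** Take 2 events per person-year and φ = 1.
- μ = 2 × 0.92 = 1.84.
- The Poisson standard error is √(1/184 + 1/92) = 0.128, so the interval around a ratio of 1 is ×/÷ exp(1.96 × 0.128) = 1.28.
- VMR = 1 + 1.84 = 2.84 and √2.84 = 1.69.
- The correct interval is ×/÷ exp(1.96 × 0.128 × 1.69) = 1.52.

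**Rare events.** At μ = 0.15 and φ = 1, VMR = 1.15 and √VMR = 1.07. At 0.05 events per person-year, √VMR is at most 1.04 even with φ = 2. The effect there is practically nil.

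**The case against.** The strongest reply has four parts.

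1. **The SAP is silent rather than wrong.** It gives outcome, covariate and exposure but does not name a variance estimator. That is so, but an analyst who follows the text and requests nothing more gets model-based standard errors. An unspecified variance in a plan is itself a gap.
2. **The size rests on assumptions.** No event rate or heterogeneity appears in either document, and with φ = 0 the Poisson interval is correct. This stands: the direction is secure wherever participants differ in event rate, but the size is not known. The 38% is the extreme corner of the range.
3. **Section 9(g) covers several models, most of them for infrequent events.** Deaths cannot recur, and serious events, grade 3–4 events, interruptions and pregnancies are likely to be few. This also stands. The material effect is on the overall event count and, depending on their frequency, drug-related events of all grades.
4. **The consequence is limited.** The listed safety endpoint (SAP 3.2.2) is at participant level, no margin or decision rule is attached to the rate ratio, the study is a pilot, and stopping rests on a combined evaluation (protocol 9.6). This keeps the point below the first rank. It does not repair the interval, which will still be reported and read as a 95% interval.

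The remedy also has limits. Robust errors were slightly above nominal in simulation, and negative binomial fits sometimes failed to converge at 0.15 events per participant.

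**Conclusion.** The concern holds. As written, SAP 9(g) gives model-based Poisson intervals on counts that include repeat events, and these are too narrow whenever participants differ in their underlying event rate. For 1 to 4 events per participant and a VMR of 1.25 to 5, the type I error is about 8% to 38% and the correct interval is 1.1 to 2.2 times as wide on the log scale. Event frequency and heterogeneity are assumed, so this is a range and not an estimate. The rate-ratio point estimate, the percentages of participants with an event and the primary endpoint are unaffected. The change should be made before the safety analysis is run.

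**What to change.** In SAP 9(g), state that every rate ratio for events that can recur will come from one of two models:
- negative binomial regression with log exposure as an offset; or
- Poisson regression with robust (sandwich) standard errors at participant level.

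Name one as the planned method. Because negative binomial fits may not converge for sparse categories, say what will be reported in that case, for example the robust Poisson interval or counts alone. Keep the planned percentage of participants with at least one event beside each rate ratio.

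The cost is one line of text and one software option, with no new data. The downside is wider intervals; if there is no heterogeneity, little is lost.

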Note: Investigators to remind females of reproductive potential of the need to avoid pregnancy while in study and adherence to the study's contraception requirements. As a reminder, females of reproductive potential who changed their minds and desire to be pregnant should be withdrawn from the study.

Note: all subjects should be reminded to take precautions to prevent transmission of HIV in accordance with national guidelines

- In addition urine home pregnancy tests for WOCBP should be performed by the patient every 4 weeks. The results should be communicated via a telephone call visit and recorded in the patient records and in the eCRF.

All subjects should return unused DTG+RPV tablets at next clinic visits for drug accountability purposes. The investigator or designee is responsible for keeping accurate up-to-date accountability documentation for the study drugs (as per pharmacy manual) such as dispensing, returns, and supply.

See Appendix 1 for details of assessment and specific visit requirements.

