6.10 Early Termination visit

In the case of early termination, every attempt will be made to ensure the subject has a termination visit. At this visit, the following evaluations and procedures are to be performed:

- Symptoms review and adverse events
- Alcohol intake, smoking habit and recreational drug use
- Total cholesterol and lipids (HDL, LDL and triglycerides) (fasted)

CONFIDENTIAL

- PBMC (Required unless exemption documented in site contract i.e. if site does not have capacity to process).
- Blood sampling for measurement of DTG & RPV (PK assessment). (Pre- or post-dose (as appropriate) at early termination visit and/or in the event of virological failure (see section 6.18). A post dose sample will be taken within 20-28 hours.
- Vital signs (pulse, blood pressure: after 10 minutes resting)
- Physical examination (symptom-directed)
- Weight
- Review of concomitant medications
- Laboratory evaluations: haematology and biochemistry (fasting) (Appendix 1)
- HIV RNA viral load
 - Note: In event of viral load failure follow section 6.18 viral failure & resistance assessment procedures.
- CD4 & CD8 count / %
- EuroQoL questionnaire
- Pittsburgh sleep questionnaire
- Patient treatment satisfaction questionnaire
- DDI assessment
- Adherence assessment (including date/time of last dose on PK days including ETV visit and/or in the event of virological failure)
- Pregnancy test for WOCBP (β -HCG).

Patients will be requested to attend for remaining visits and complete study assessments to week 96 even if they are no longer taking study medication.

See Appendix 1 for details of assessments.

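### SAP 9(g) puts the pregnancy rate over the person-time of all participants, men included; it should use only women of child-bearing potential

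*SAP*

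**What the plan says.** SAP 9(g) lists the safety events and ends the list with pregnancy and death: "treatment interruption due to AE (all grades), pregnancies and death will be summarized with descriptive statistics". It continues: "The incidence rates of the events defined above will be compared between the treatment groups using a Poisson regression analysis". The model is described first as one "which accounted for all adverse events and follow-up duration for each participant", and then as containing "the number of events, the treatment group and the duration of exposure in year in log". On presentation it says: "A table will summarize the frequency of adverse events and pregnancies". The columns of that table include the number and percentage of patients with the event, the rate per 100 person-years in each group, and the rate ratio with its confidence interval. A count and percentage for pregnancy are also promised, with no denominator stated.

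The safety population (SAP 6.3.4) is everyone in the modified intention-to-treat population with at least one dose, without restriction by sex. Protocol 5.1 admits men, and women who are post-menopausal or surgically sterile. Pregnancy is looked for only in women of child-bearing potential. Besides the tests at visits, Protocol 6.8 says that "urine home pregnancy tests for WOCBP should be performed by the patient every 4 weeks".

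**The concern.** A rate per person-year describes risk only if the person-time belongs to people who can have the event. Men and women who cannot conceive add time to the denominator and can add nothing to the numerator. The risk table in Protocol 1.1 singles out neural tube defects with dolutegravir and plans pregnancy monitoring every four weeks, so readers will look for the pregnancy rate. A rate over all participants would look lower than the rate among the women concerned, by a factor that depends on the sex and age mix of the trial.

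There is also a smaller question of definition. The same paragraph gives the adverse-event person-time two names and no start or stop date, so the analyst could choose the period after seeing the data.

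**Working it through.** The plan states no safety rate, so there is no figure to reproduce. The working has three steps.

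**1. Dilution of the pregnancy rate**

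Inputs: 100 participants in the DTG/RPV arm and 50 in control (SAP 5); 96 weeks of follow-up; f not given, so assumed.

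- Rate over all participants = k / T, with k pregnancies and T total person-years.
- Rate over women of child-bearing potential = k / (fT).
- Understatement factor = (k / fT) / (k / T) = 1/f.

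Example: one pregnancy in the DTG/RPV arm, with everyone completing. T = 100 × 96 / 52.18 = 184 person-years, so the all-participant rate is 100 × 1/184 = 0.54 per 100 person-years.

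| Assumed f | Person-years at risk | Rate per 100 person-years | Factor |
|---|---|---|---|
| 10% | 18.4 | 5.44 | 10 |
| 20% | 36.8 | 2.72 | 5 |
| 30% | 55.2 | 1.81 | 3.3 |

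The factor does not depend on the length of follow-up. A percentage over all participants is diluted in the same way: 1/100 = 1%, against 1/20 = 5% if 20 of the 100 are women of child-bearing potential.

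**2. Effect on the rate ratio**

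All-participant ratio / correct ratio = f₁ / f₀, where f₁ is the share in the DTG/RPV arm and f₀ the share in control. With equal shares this is 1 and the ratio is undistorted. Chance imbalance at 100 against 50 was simulated as Binomial(100, f)/100 divided by Binomial(50, f)/50, with 200,000 draws:

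| Assumed f | Median f₁/f₀ | 95% range |
|---|---|---|
| 10% | 1.00 | 0.36 to 4.00 |
| 20% | 1.00 | 0.53 to 2.25 |
| 30% | 1.00 | 0.61 to 1.80 |

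So there is no systematic bias, but a single trial could be well off.

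**3. Adverse-event person-time: the passages side by side**

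- Collection: "The adverse event reporting period will be from consent until" the final visit (Protocol 8.2.3). Screening is up to 28 days before randomisation (Protocol 6.4), and the closing phone contact is 30 days after week 96 (Protocol 6.9). Participants who stop early are asked to "complete study assessments to week 96 even if they are no longer taking study medication".
- Serious events and pregnancies: a different window, from consent to 28 days after treatment stops (Protocol 8.3.1).
- Denominator: follow-up duration in one sentence of SAP 9(g), duration of exposure in the next.
- If both mean follow-up from baseline, time off drug is in the denominator too. Only events between consent and baseline could lack matching time.
- If exposure meant time on drug, the most extreme completer would have (28 + 672 + 30) / 672 = 1.086, that is +8.6%.
- 9(g) does not say whether rates run to week 48 or week 96. Controls with virological success switch to DTG/RPV at week 48 (SAP 4.1). For such a control who completes, (96 − 48)/96 = 50% of the time is therefore on the experimental drug.

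**The case against.** **On pregnancy.** The SAP never instructs anyone to include men; it omits a restriction, and a careful programmer might add it. Contraception is required and women planning pregnancy are excluded, so few pregnancies are likely, and a rate ratio would say little with either denominator. Every pregnancy is followed to outcome (Protocol 8.3.1, Table 2), so detection of harm does not rest on this rate, and SAP 3.2.2(g) does not list pregnancy as an endpoint. All of this limits the consequence. It does not remove the point: the table in 9(g) calls for the rate, one per-participant offset is named, and no other section narrows it.

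**A stronger reading on adverse events.** A reader might infer that events from consent to the last contact are divided by time on drug only, so that adverse-event rates are overstated. The documents do not support this. The sentence just before the offset speaks of each participant's follow-up duration, exposure is the usual name for a Poisson offset, and nothing limits it to treatment. Nor does 9(g) say that every event since consent enters the count. The +8.6% above needs that reading and a full 28-day screening period. Carrying it over to early stoppers would also give them the 30-day contact that Protocol 6.9 does not require of them. What stands is that the at-risk period is undefined.

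**A stronger reading on the rate ratio.** A reader might also infer that the pregnancy rate ratio is biased. It is not, unless the share of women of child-bearing potential differs between arms.

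**Conclusion.** The pregnancy point holds. As written, SAP 9(g) yields a pregnancy rate too low by 1/f: 10, 5 or 3.3 times for assumed shares of 10%, 20% or 30%. The size is conditional, because the documents give no share; the direction is certain whenever the trial includes anyone who cannot become pregnant. Distortion of the rate ratio is possible through chance imbalance but not inherent.

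The adverse-event person-time calls for clarification only. An overstatement of adverse-event rates is not established.

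Both matters concern descriptive safety results.

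**What to change.** In SAP 9(g), state that the percentage, rate and rate ratio for pregnancy are computed on women of child-bearing potential and their person-time only.

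In the same paragraph, as a clarification:

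- Use one term for the person-time. Define one at-risk period starting at baseline, with a stated end and stated handling of time after early stopping. Set the end for serious events and pregnancies with their shorter reporting window in view.
- Count only events with onset inside that period; list pre-baseline events separately.
- Make the between-arm comparison over baseline to week 48, and report control-arm time after the switch separately. An offset running to the last assessment by randomised arm would count control time on DTG/RPV as control time.

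The cost is a few sentences and some programming. Child-bearing potential is already a baseline variable (SAP 7.3), event onset is recorded (Protocol 8.2), and treatment start and stop dates are kept (Protocol 10.1.2). The price is that screening events leave the comparison, and the pregnancy rates will have wide intervals because they rest on fewer person-years.
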